7.2 Study Entry Criteria

7.2.1 Inclusion Criteria

A subject will be eligible for study participation if the subject meets all of the following criteria:

- 1. Provides written informed consent to participate in the study, is able to understand the procedures and study requirements, and agrees to abide by the study restrictions and return for the required study assessments.
- 2. Male or female outpatients, 18 to 65 years of age, inclusive.
- 3. Currently meets the DSM-5 criteria for MDD without psychotic features, based on the SCID-

5-CT, with a current major depressive episode of at leave 4 weeks in duration at Visit 1.

- 4. MADRS score of ≥ 25 and CGI-S ≥ 4 at Screening (Visit 1) and Baseline (Visit 2).
- 5. Normal physical examination findings and clinical laboratory test results from Screening (Visit 1) or abnormal results that are judged not clinically significant by the investigator.
- 6. Body mass index (BMI) between 18 and 40 kg/m², inclusive.
- 7. If female of childbearing potential, having a negative urine pregnancy test result at Visit 1 and Visit 2, and practicing an adequate method of birth control (e.g. oral or parenteral contraceptives, intrauterine device, double-barrier) and does not plan to become pregnant during the course of the study. Long-term abstinence is acceptable as long as the subject agrees to use double-barrier contraception if they decide to have sexual intercourse. Female subjects using a hormonal contraceptive or intrauterine device must have been doing so for at least 1 month before Screening and must follow that product's package insert instructions including additional protection at times when hormonal contraceptive doses might be missed. Female subjects may be included without a negative urine pregnancy test if they are surgically sterile or at least 2 years post-menopausal. Male subjects and their female sexual partners should use an acceptable method of birth control (as noted above) during the study.

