- 21. Any current or recent medical, psychiatric, or social condition that, in the investigator's opinion, is likely to interfere with the conduct of the study, confounds the interpretation of study results, or endangers the subject's well-being. This includes (but is not limited to) any clinically significant oncologic, hematologic, endocrine/metabolic, cardiovascular, respiratory, renal, hepatic, gastrointestinal, infectious or neurologic disease or has a chronic disease which is unstable or progressive.
- 22. Hypertension defined as resting, sitting systolic blood pressure (BP) ≥150 mm Hg or diastolic blood pressure ≥ 95 mm Hg. Patients with high BP (as defined above) may be accepted in the study if they subsequently have acceptable BP values on reassessment at least 30 minutes apart.
- 23. Hypo- or hyperthyroidism, unless stabilized on appropriate pharmacotherapy with no change in dosage for at least 1 month before Visit 1 (Serum TSH must be > 0.75 × the LLN and < 1.25 × ULN).
- 24. History of allergy or hypersensitivity to bupropion, dextromethorphan, opiate drugs (e.g. codeine, etc.), or any other ingredient in the study drug.
- 25. History of intolerance to bupropion or dextromethorphan.
- 26. Patients who have received dextromethorphan co-administered with quinidine (e.g. Nuedexta[®]) within the past four weeks.
- 27. Gastric bypass or any condition that would be expected to affect drug absorption (lap band

procedures are acceptable if there is no problem with absorption).

- 28. Narrow-angle glaucoma without a patent iridectomy.
- 29. Known human immunodeficiency virus (HIV) infection.
- 30. Clinically significant signs of active hepatitis B and/or C infection.
- 31. Screening liver enzyme test (e.g., bilirubin, aspartate aminotransferase and/or alanine aminotransferase) results > 2.0 x ULN.
- 32. Any clinically significant abnormality on the screening laboratory tests, as assessed by the study investigator and/or the medical monitor.
- 33. Treatment with any investigational drug within 30 days of Visit 1.
- 34. Currently hospitalized or residing in an in-patient facility during the study.
- 35. Unable or unlikely to comply with the study protocol or unsuitable for any other reason, including other conditions that might indicate that the subject is unsuitable for the study as judged by the investigator such as known history of poor medication compliance or significant instability in status of psychosocial issues.

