12.4.3.2 Clinical Laboratory Evaluations

For continuous laboratory parameters, descriptive statistics will be presented for each visit and for the changes from Baseline to each subsequent visit by treatment group.

Additionally, clinical laboratory parameters will be categorized as low, normal, or high according to laboratory range specifications and the number and percentage of subjects in each category will be presented in shift tables.

Laboratory values that are outside the normal range will also be flagged in the data listings, along with corresponding normal ranges.

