# **10.0** SUMMARIES OF MEASURES OF SAFETY

Safety analyses will be performed for the safety population. Safety evaluations will be based on the incidence, severity, relatedness, and type of adverse events, as well as on clinically significant changes in the subject's physical examination, vital signs, and clinical laboratory results. Safety variables will be tabulated and presented by study drug actually received.

Because there is no pre-specified safety outcome defined in terms of AEs, clinically relevant laboratory parameters, or vital signs, any formal comparisons between the treatment arms with respect to specific safety parameters will be post-hoc.

C-SSRS (Columbia - Suicide Severity Rating Scale) will be summarized as a safety assessment.

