#### **10.2** ADVERSE EVENTS

Each AE and SAE term recorded on the case report forms (CRFs) by primary system organ class (SOC) will be mapped to a preferred term using the MedDRA dictionary. The investigator will assess AE severity and relationship to the study treatment.

A treatment emergent adverse event (TEAE) is defined as any AE with an onset date on or after date of randomization, or any ongoing event on the date of first dose that worsens in severity after date of randomization. Only non-serious TEAEs with an onset date prior to date of last dose and serious TEAEs

AXSOME Therapeutics, Inc. AXS-05-MDD-201 SAP CONFIDENTIAL Page 13 of 16 Version 1.0—11 December 2018

with an onset date prior to date of the final visit + 30 days will be tabulated in summary tables. However, all AEs recorded will be listed. For the purpose calculating treatment emergence and inclusion in summary tables, incomplete onset dates will be imputed as detailed in Appendix A.

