## **10.3** LABORATORY ASSESSMENTS

Chemistry and Hematology, Urinalysis and Coagulation Profile will be assessed at Screening and Week 6. Summary statistics for these parameters will be presented by visit for the actual value and change from baseline for each test in each laboratory category (Hematology, Chemistry, Urinalysis, and Coagulation Profile). Shift tables will be presented for shifts from baseline lab categories to end of study laboratory category. The three laboratory categories will be: L (below lower bound of normal range), N (within normal range), and H (above higher bound of normal range).

If a lab value is reported using a non-numeric qualifier (e.g., less than ( $\leq$ ) a certain value, or greater than (>) a certain value), the given numeric value will be used in the summary statistics, ignoring the non-numeric qualifier.

If a subject has repeated laboratory values for a given time point, the value from the first evaluation at that time point will be used for summarization purposes. For the purpose of determining baseline, the last nonmissing observation on or prior to randomization will be used. The Week 6 values will be the last post-baseline value on or prior to Week 6.

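### No planned table counts subjects with a marked liver-test rise: the only categorical laboratory summary is an ungraded low/normal/high shift, and subjects may enter already high

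*SAP*

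**What the plan says.** **Entry.** Protocol 7.2.2, exclusion 31, removes subjects with "Screening liver enzyme test (e.g., bilirubin, aspartate aminotransferase and/or alanine aminotransferase) results > 2.0 x ULN". Exclusion 32 also removes "Any clinically significant abnormality on the screening laboratory tests, as assessed by the study investigator and/or the medical monitor", while inclusion 5 (Protocol 7.2.1) admits "abnormal results that are judged not clinically significant by the investigator". A raised liver test of up to 2.0 × ULN is therefore compatible with entry, provided it is judged not clinically significant.

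**Categorical analysis.** SAP 10.3: "The three laboratory categories will be: L (below lower bound of normal range), N (within normal range", and H above the range. The shift runs from baseline to end of study. Protocol 12.4.3.2 plans the same: "clinical laboratory parameters will be categorized as low, normal, or high according to laboratory range specifications". Neither text subdivides H.

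**Other laboratory output.** SAP 10.3 also summarises the actual value and the change from baseline for each test by visit. SAP 6.0 defines those summaries as n, mean, SD, median, minimum and maximum. Protocol 12.4.3.2 flags out-of-range values in the listings beside their normal ranges.

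**Timing.** The scheduled panels are at Screening and at Visit 8/ET (Protocol 17.2). Unscheduled repeats are allowed (Protocol 9.3.3.2.1). SAP 10.3 takes the last post-baseline value up to Week 6 as the Week 6 value and, where a time point has repeats, the first of them.

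**Adverse events.** Protocol 9.3.3.2.4 requires laboratory changes that the investigator finds clinically relevant to be reported as AEs. SAP 10.2 limits which of them reach the tables: "Only non-serious TEAEs with an onset date prior to date of last dose", plus serious events over a longer window.

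**The concern.** SAP 10.0 rests the safety evaluation partly on "clinically significant changes in the subject's physical examination, vital signs, and clinical laboratory results". The one laboratory table that counts subjects cannot separate a large change from a trivial one. A subject who enters in H has no higher class to move to. For everyone else, H pools a value just above the ULN with any higher multiple.

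The protocol's sole objective (Section 5) is safety and tolerability, and it convenes no data safety monitoring board (Section 11). The by-arm tables therefore carry much of the laboratory message. Two arms could show equal N to H counts while one of them held several subjects above 2.0 × ULN, the level the protocol itself treats as too high for entry. A reader of the tables could not tell.

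**Working it through.** The plan states no figure on this point, so there is none to reproduce. The check applies the SAP's rules to example values.

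**Inputs**
- Entry limit 2.0 × ULN: Protocol 7.2.2, exclusion 31 ("alanine aminotransferase) results > 2.0 x ULN"), with the clinical-significance filter of inclusion 5 and exclusion 32.
- Classes L, N and H with no grading inside H: SAP 10.3, Protocol 12.4.3.2.
- Size: 30 per arm, 60 in total (Protocol 12.2). This is a target for compliant completers. The Safety Population is everyone dosed, so it may be larger.
- Share entering with a liver test in H: not given. Assumed 5–15%, with 2–20% as an outer range.

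**Step 1: the shift rule.** A value up to 1 × ULN is N (taking all examples to be above the lower bound); a value above 1 × ULN is H.

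| Baseline (× ULN) | End of study (× ULN) | Change | Ratio | Shift cell |
|---|---|---|---|---|
| 1.5 | 8 | +6.5 | 5.3 | H to H |
| 1.9 | 10 | +8.1 | 5.3 | H to H |
| 2.0 | 5 | +3.0 | 2.5 | H to H |
| 0.98 | 1.02 | +0.04 | 1.04 | N to H |
| 0.35 | 0.99 | +0.64 | 2.8 | N to N |

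The three largest rises register no shift, and the smallest one does.

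**Step 2: the planned summary statistics.** Suppose one subject of 30 rises by 8.1 × ULN and 29 do not change.
- Mean = 8.1 / 30 = 0.27.
- SD = √[(8.1² − 30 × 0.27²) / 29] = √(63.42 / 29) = 1.48.
- Median = 0; maximum = +8.1.

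The maximum shows the case. Now suppose five subjects rise by 8.1.
- Mean = 5 × 8.1 / 30 = 1.35.
- The median is still 0 and the maximum is still +8.1.

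The mean and SD move, but no planned statistic says whether one subject or five were affected.

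**Step 3: which value is used.** The shift uses the last value, and there is no worst-value rule. An unscheduled peak that has fallen by Visit 8 enters neither the shift nor the Week 6 summary.

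**Step 4: the AE tables.** Unused drug is collected at Visit 8/ET (Protocol 9.1.5), so the last dose falls on or before that date. A non-serious AE dated from that visit's sample does not start before the last-dose date, and SAP 10.2 leaves it out of the summary tables. It is listed but not counted. A serious event, or one that the investigator dates earlier, is still tabulated.

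**Step 5: how many subjects.** Expected number entering high = 60 × share; chance of at least one = 1 − (1 − share)^60.

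| Assumed share | Expected of 60 | Chance of at least one |
|---|---|---|
| 2% | 1.2 | 70% |
| 5% | 3 | 95% |
| 10% | 6 | 99.8% |
| 15% | 9 | about 100% |
| 20% | 12 | about 100% |

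The pooling inside H applies whatever this share is.

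**The case against.** A reader might infer that liver tests are analysed only by class, so that a large rise would vanish. The documents do not support that. The sentence in SAP 10.3 just before the shift tables plans actual-value and change summaries for every test, and their maximum is a measure of size. The protocol's flagged listing would show the same subject. A clinically relevant rise found in mid-study must be reported as an AE, and with onset before the last dose it would be tabulated. That covers many of the peaks in Step 3.

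Other parts of the defence also stand. The SAP follows the protocol here, so there is no contradiction between the two on the shift table. No AE of special interest is defined (Protocol 10.3.1), no formal safety comparison is planned (Protocol 12.4.3), and nothing in the documents points to a hepatic concern. The clinical-significance filter narrows who can enter high. The Visit 8/ET gap in the AE tables comes from the SAP 10.2 cut-off, which affects every type of non-serious AE and conflicts with Protocol 12.4.3.1, where the window runs to 7 days after the last dose. That is a separate matter. Any single cut-point, 2.0 × ULN included, also produces its own boundary cases.

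The defence does not supply a count. A maximum describes one subject, and a listing gives no number per arm. The general allowance in SAP 10.2 for further safety analyses as appropriate prespecifies nothing.

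**Conclusion.** The point holds as a reporting gap of minor to moderate weight. The only categorical laboratory analysis is an ungraded shift to the last value up to Week 6. A marked rise in a subject who entered above the ULN is tabulated as H to H, and no table gives the number of subjects per arm with a marked rise. It would not be right to say that the plan hides such a rise: it would appear as a maximum, in a flagged listing or, depending on its date and seriousness, in the AE tables.

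At an assumed 5–15% of about 60 subjects, 3–9 could not register any worsening in the shift table. That share is an assumption, and the base of 60 is the completer target. No figure stated in either document changes.

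**What to change.** Keep the shift table. Add to SAP 10.3 one descriptive table for the Safety Population giving the number and percent of subjects per arm whose worst post-dose ALT, AST or total bilirubin exceeds 2.0 × ULN. Scheduled, early-termination and unscheduled values should all count. For each subject counted, show the baseline and the worst value as multiples of ULN, so that 1.9 to 2.1 can be told from 1.9 to 10.

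The limit is borrowed from exclusion 31 because a subject entered under that criterion was not above it at Screening, so a later value above it is new since then. It serves for reporting only and is not a clinical rule.

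The cost is a sentence in the SAP and one table from results and reference ranges already collected, with no change to visits or procedures. The downside is a cut-point that is itself arbitrary, which showing both values softens.

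Separately, the AE cut-off in SAP 10.2 and the window in Protocol 12.4.3.1 should be reconciled.

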## **10.4** VITAL SIGNS

Vital signs will consist of blood pressure (systolic and diastolic blood pressure, mmHg), pulse rate (beats per minute), and respiratory rate (breaths/min), collected while sitting, following a rest period of at least 3

AXSOME Therapeutics, Inc. AXS-05-MDD-201 SAP CONFIDENTIAL Page 14 of 16 Version 1.0—11 December 2018

minutes. Vital sign values and change from baseline in the vital signs will be summarized for each treatment group.

## **10.5** PHYSICAL EXAM

Number and percent of subjects with abnormal physical exam findings at Screening will be summarized by body system for each treatment group and overall. Physical Exam data for each subject will also be presented in a listing.

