9.1.5 Visit 8 (Day 42) / Early Termination

The following procedures will be performed at Visit 8 (Days 42) or the Early Termination Visit:

- Record vital signs, including: Blood pressure, pulse, respiratory rate, and oral temperature after subject has been seated for 5 minutes.
- Record weight.
- Review and record AEs since last visit.
- Review and record any current concomitant medication use (including OTC, vitamins, and supplements).
- Perform a physical examination (excluding breast and genitourinary examination) with review of body systems.
- Collect blood and urine samples for central clinical laboratory tests (hematology, serum chemistry, urinalysis, thyroid panel, and serum ethanol); see Section 9.3.3.2.1 for a complete list of required laboratory tests.
- Collect urine for an on-site urine pregnancy test (if female).

•

- Collect all unused study drug dispensed at previous visit.
- Assess study drug compliance via drug accountability. Noncompliant subjects may be discontinued.
- •
- Administer evaluations:
 - \circ MADRS
 - o QIDS-SR-16
 - o CGI-S
 - o CGI-I
 - C-SSRS (since last visit)

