9.3.3.3.2 Physical Examination

A complete physical examination (excluding breast and genitourinary examination) will be performed at Screening by a licensed physician or clinician (NP, DO, PA) and at the final on-site visit (Visit 8/ET). Physical examination will include assessments of head, eyes, ears, nose, throat, lymph nodes, skin, extremities, respiratory, gastrointestinal, musculoskeletal, cardiovascular, and nervous systems. The physical examination should be performed by the same person each time, whenever possible. Physical examination abnormalities determined by the Investigator to be clinically significant at Screening should be recorded as medical history. The thoroughness of the Visit 8/ET physical examination is at the discretion and judgment of the Investigator, but should include a brief review of systems to ensure there have been no changes since Screening.

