12.1.1 Safety Endpoints

Safety endpoints include the following:

- Adverse Events (AE)
- Adverse Dropouts (ADOs)
- Incidence of Treatment Emergent Adverse Events (TEAEs)
- Clinical laboratory test results
- Vital sign measurements
- Physical examination findings
- Columbia Suicide Severity Rating Scale (C-SSRS)

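### SAP 10.5 summarises physical-examination findings by arm only at Screening, before dosing, so the changes that SAP 10.0 says safety rests on have no defined on-treatment summary

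*SAP*

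**What the plan says.** Protocol 12.1.1 includes "Physical examination findings" among the safety endpoints. The examination is scheduled twice: at Screening, and at Visit 8 or early termination. The Visit 8/ET procedures in Protocol 9.1.5 read "Perform a physical examination (excluding breast and genitourinary examination) with review of body systems". Protocol 9.3.3.3.2 leaves the depth of that second examination to the investigator but says it "should include a brief review of systems to ensure there have been no changes since Screening".

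For the output, Protocol 12.4.3.4 commits only to listings. SAP 10.0 goes further. It says the safety evaluation will draw on "clinically significant changes in the subject's physical examination, vital signs, and clinical laboratory results", and that safety variables will be tabulated according to the drug the subject actually received. SAP 10.5 then defines two outputs. The first is a table: "Number and percent of subjects with abnormal physical exam findings at Screening will be summarized by body system for each treatment group and overall". The second is a listing: "Physical Exam data for each subject will also be presented in a listing". No other SAP section mentions a physical-examination summary.

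**The concern.** The general statement in SAP 10.0 is about change. The specific section that should deliver it tabulates a single time point at which no subject has taken study drug. A difference between arms in that table can reflect only chance imbalance at baseline. Eligibility narrows its content further: inclusion criterion 5 admits only subjects whose examination is normal or who have "abnormal results that are judged not clinically significant by the investigator".

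The examination that could show an effect of treatment is the one at Visit 8/ET, and no by-arm count is defined for it. Safety and tolerability is the only objective stated in Protocol section 5, and no formal safety comparison is planned, so descriptive tables carry the main message of the safety report. If the plan is followed literally, a reader of the report would find under the physical-examination heading a baseline table and a listing to be counted by hand.

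**Working it through.** No arithmetic decides this point. The check sets the sections side by side.

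**1. Is the table entirely pre-dose?** Protocol 9.1.1 puts Screening at Days -28 to -1. Randomisation is at Visit 2 (Day 0), and the Schedule of Assessments has dosing start on the morning of Day 1. Every finding in the SAP 10.5 table therefore precedes the first dose.

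**2. What is specified for the repeat examination?**

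| Output | By-arm summary? | Reflects exposure to study drug? |
|---|---|---|
| SAP 10.5 table, Screening | Yes | No |
| Table at Visit 8/ET | Not defined | – |
| Table of change or shift since Screening | Not defined | – |
| SAP 10.5 listing | No, subject level | Yes, for the Visit 8/ET records |

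**3. How are the neighbouring safety domains treated?** SAP 10.3 handles laboratory tests, which are also taken at Screening and Week 6. It gives them change from baseline and shift tables from baseline to end of study. SAP 10.4 gives vital signs a summary of change by treatment group. Of these three domains named in SAP 10.0, only the physical examination has no post-baseline summary.

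**4. Do the adverse-event tables fill the gap?** They do so in part. Protocol 10.2.1 makes any clinically relevant observation at a visit an adverse event, and SAP 10.2 tabulates treatment-emergent events by arm. But SAP 10.2 keeps non-serious events in the summary tables only when onset is before the date of last dose. The dates are:

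- The planned last dosing day is Day 42.
- Visit 8 is Day 42 ± 2, that is Day 40 to Day 44.
- Unused drug is collected at Visit 8 and none is dispensed there, so the last dose ordinarily falls on or before the visit day.

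A non-serious finding whose onset is dated to Visit 8 is then not before the last dose, and it drops out of the TEAE tables. The same holds at an ET visit made after dosing has stopped. If the investigator can date the onset to an earlier day on treatment, the finding stays in. By contrast, Protocol 12.4.3.1 counts non-serious events up to 7 days after the last dose, so a finding dated at Visit 8 would normally qualify under the protocol's window and be lost only under the SAP's.

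**5. Where does such a finding end up?** It appears in the adverse-event listing, since SAP 10.2 lists all recorded events, and in the physical-examination listing. It appears in no by-arm summary.

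**The case against.** The strongest defence is that the SAP already exceeds the protocol. Protocol 12.4.3.4 planned listings alone, and naming an item as a safety endpoint does not promise a table. SAP 6.0 arranges listings by study drug, centre and subject and has them cover all CRF data, so Visit 8/ET findings will be laid out by treatment. With a target of 30 compliant completers per arm, they can be reviewed by eye. SAP 10.2 also leaves room for further safety analyses as appropriate. All of this stands. What remains is that SAP 10.0 promises tabulated change and SAP 10.5 does not define it.

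A second defence is that anything clinically relevant becomes an adverse event, so what escapes is by rule not clinically relevant. That is a fair reading of Protocol 10.2.1, but the onset cut-off in SAP 10.2 weakens it at the very visit where the examination is repeated. The cut-off is a matter for SAP 10.2 and needs its own correction. A table in SAP 10.5 does not repair it.

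A third defence concerns the data. The Screening examination is complete, while the later one may be brief. A simple normal/abnormal cross-tabulation would mix change in the subject with change in examination depth. This objection stands and shapes the fix below.

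A reader might infer something stronger: that the trial cannot report on-treatment examination findings by arm, or that some 60 examinations are lost. The documents do not support either. The data are listed by treatment, and the relevant findings are captured as events. Sixty is the planned number of compliant completers, not the number of Visit 8/ET examinations, which would also include those of subjects who terminate early or are replaced.

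**Conclusion.** The point holds as a minor gap between two parts of the SAP. SAP 10.0 bases safety on examination changes tabulated by drug received. The only by-arm table in SAP 10.5 is pre-dose, and the number of defined by-arm summaries of on-treatment examination findings is zero. The SAP does not fall short of Protocol 12.4.3.4, and no data are lost. The primary analysis and the sample size are untouched.

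The practical exposure is narrow: new or worsened abnormalities first noted at Visit 8/ET that are non-serious and dated to that visit, together with abnormalities not judged clinically relevant. The documents give no expected frequency for either, so no number can be put on how many would be affected.

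The conclusion assumes that the general tabulation sentence in SAP 10.0 does not stand in for an unstated table, and that no other specification, such as a set of table shells outside these documents, already provides one.

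**What to change.** In SAP 10.5:

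- Keep the Screening table and label it a baseline description.
- Add one descriptive table for Visit 8/ET, in the Safety Population, by body system and treatment received. It gives the number and percentage of examined subjects with an abnormality that is new or worse since Screening.
- Use as the denominator for each body system the subjects examined for that system at Visit 8/ET, and show the number not examined on a separate line.
- State that no formal comparison is made, in line with Protocol 12.4.3.

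The cost is one table and no additional examination. It assumes that the CRF records the Visit 8/ET examination by body system and separates a normal result from a system not examined. Normal/abnormal codes identify a new abnormality but not a worsened one. If the CRF does not record worsening, the rule for judging it from the recorded descriptions should be fixed before unblinding.

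The downside is uneven examination depth. Denominators will vary by system, a briefer second examination can miss abnormalities, and a change from abnormal to normal should not be read as improvement. Counting only new or worsened findings limits this problem but does not remove it.

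Separately, the non-serious onset cut-off in SAP 10.2 should be reconciled with the window in Protocol 12.4.3.1, so that an examination finding recorded as an adverse event at Visit 8 is not left out of the TEAE tables.
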